6.5.5.6 Time of Diagnosis Clinic Visit

If a subject is diagnosed with clinically-apparent RA (as defined in protocol section 2.1, *Primary Objective*) prior to the Month 36 visit, the subject will return for a Time of Diagnosis visit, which will supersede any regularly scheduled visit with which it overlaps. During the Time of Diagnosis visit the following evaluations will occur:

1. Demographics
2. Concomitant Medications
3. AE Assessment (see Section 7.3.2, *Collection Period*)
4. Physical Exam (full)
5. Vital Signs including heart rate and sitting systolic/diastolic blood pressure and weight and waist circumference
6. Subject Questionnaires
 - Profile 29 v2.0
 - Epidemiologic Questionnaire
 - Dietary Assessment Questionnaire
 - Self-reported Joint Symptoms, including modified MDHAQ
 - Evaluate family member participation
7. Joint Examination – Physician’s Assessment (including a swollen/tender joint count). *Note: The count will include 66 tender/64 swollen joints.*
 - *The ankle joint(s) on each limb will be counted as a single joint that includes the talo-tibial joint (also called the talo-crural joint), subtalar joint (also called talo-calcaneal joint), and inferior tibio-fibular joint.*
 - *The midfoot joints will not be evaluated for either tenderness or swelling.*
 - *The hip joints will not be evaluated for swelling.*
8. Specimen collection for **future** core outcome testing (hsCRP, IgM-RF, and anti-CCP3) and serum for mechanistic studies will be completed.
9. Specimen collection for mechanistic studies: PBMC, plasma, RNA, and urine. *Note: DNA will be collected from subjects who consent to future genetic testing.*
10. Specimen collection for HCQ Level analysis
 - *Note: This specimen will be collected at the Time of Diagnosis visit if the specimen was not collected previously and the visit occurs during the treatment period.*
11. Discontinue study therapy
12. Pill Counts (if subject is diagnosed during the treatment period)
13. Refer subject to clinical care

14. Encourage subject to return for all remaining planned study visits. See Section 6.5.9, *Evaluations Triggered by a Swollen Joint*, for testing that will no longer be completed at post-diagnosis visits.

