- After the Time of Diagnosis visit, biologic samples (blood, urine) for mechanistic specimens and core outcome specimens (anti-CCP3, IgM-RF, and hs-CRP) will not be collected and the dietary and epidemiologic questionnaires will not be completed.
- Routine safety labs samples will be collected at Week 24 and Week 52 regardless of subject diagnosis and prohibited medications.
- HsCRP will be collected at Week 52 and Month 36.

Note: See Appendix 15.2.1, *Evaluations Triggered by a Swollen Joint Flow Chart*, for a figure containing the information noted above.

- 3) If a swollen joint consistent with RA-like synovitis is identified by joint examination, but the ACR/EULAR score is <6 , and no erosions are observed on the x-ray, the subject will be informed of this at the 3-6 week follow-up visit, and the following will occur:
 - The subject will be instructed to continue taking the study therapy.
 - The subject will be instructed to return to the clinic every 6 weeks (for either an unscheduled visit or a regularly scheduled visit that falls within the next 6 weeks) until:
 - The synovitis resolves and is not present at two consecutive visits (unscheduled or planned) 6 weeks apart, then the subject will resume routine interval study visit follow-up with routine core outcome testing and mechanistic specimen draws.
 - The subject develops definite RA by 2010 ACR/EULAR Classification Criteria or erosions on follow-up x-rays then the follow-up visit will become a Time of Diagnosis visit as outlined above (refer to Section 6.5.5.6, *Time of Diagnosis Clinic Visit*).

- *Note:* If synovitis persists but does not meet 2010 ACR/EULAR Classification Criteria for RA, x-rays may be repeated at 6-month intervals to assess for development of erosions provided the subject is not pregnant. If a swollen joint(s) that is consistent with RA-like synovitis is identified during the joint examination during the 3-6 week follow-up visit, follow blood draws according to Appendix 15.2.1, *Evaluations Triggered by a Swollen Joint Flow Chart*.

6.5.10 Procedures for Subjects Diagnosed with Inflammatory or Rheumatoid Arthritis by an Outside Physician

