8.3.3 Mechanism/Immunological Analysis

Descriptive statistics and plots (including, but not limited to, those described subsequently) will be used to gain an understanding of the data prior to developing any statistical models. Means, medians, standard deviations, minimums, and maximums will be computed for each continuous biomarker at each time point for treatment groups and separately for subjects who do/do not experience clinically significant disease reactivation. For dichotomous biomarkers (i.e. + or -), frequencies and percents will be computed at each time point for treatment groups and separately for subjects who do/do not experience clinically-apparent RA. In addition, the biomarkers can be treated as ‘counts’ – for example, the number of autoantibodies positive in the ACPA array, and then analyzed as continuous variables to test a hypothesis that HCQ treatment results in decreased number of ACPAs. To gain a better understanding of trends over time, summary statistics (e.g., means, medians, or percents) will be plotted versus time at the relevant time points. Plots for individual subjects may also be useful.

Multivariate model may be considered to evaluate the relationships between treatment group and alterations of biomarkers that may suggest improved underlying autoimmunity and/or inflammation.

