Population Level Summary: At each planned clinic visit, the number, and percent of individuals with self-reported joint symptoms will be computed by treatment arm, and separately for those with and without a prior study-confirmed diagnosis of CL- RA. Among those with symptoms, mean, median, min and max # of affected joints will also be reported. Summary statistics will also be plotted over time to gain a better understanding of trends.	Analysis: At Week 52 and Month 36/EOS, Mann-Whitney U statistics will be used to compare joint counts between treatment arms, separately for those with and without a diagnosis of CL-RA. Because the distributional characteristics of these variables are unknown, we cannot prespecify the planned analysis strategy. However, in this population, it is reasonable to expect there will be excess # of participant visits where no joint symptoms are reported. If this is the case, it may appropriate to fit a longitudinal zero-inflated negative binomial model with the number of involved joints as the dependent variable and treatment arm as the primary fixed effect. Important additional fixed effects to consider would include prior CL-RA diagnosis at time of assessment (Y/N), study day (or visit), treatment period (on study drug vs off study drug), duration on study treatment, and interaction terms for treatment arm, prior CL-RA diagnosis, and study day (or visit). Heterogeneous random participant effects could be included in the model per the methods of Zhu et al [4], and relevant covariates included in the regression on the covariance matrix will be determined. T-tests for the maximum likelihood estimates of the model parameters could be used to determine the significance of the parameters to the model.
Note: Modeling will be exploratory and only initiated if descriptive analyses suggest interesting trends.	

8.3.7. Study Objective 8

Study Objective 8 is to explore underlying immune responses over time in the early natural history of RA development and in response to HCQ therapy through measurement of a variety of biomarkers. Endpoints will be laboratory test results from mechanistic specimens collected at specified clinic visits during the study.

Table 15: Estimands of Study Objective 8

Estimand Label	Biomarkers and immune response variables
Secondary 8.1	Levels of anti-CCP3 over time
Secondary 8.2	Levels of IgM-RF over time
Secondary 8.3	Levels of hsCRP over time

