Population: mITT	IES Policy: All available study data will be included.
Population Level Summary: Summary statistics and plots will be used to gain an understanding of the data prior to developing any statistical models or hypothesis tests.	Analysis: Inferential analyses will be considered if descriptive analyses suggest interesting trends.

For categorical variables, frequencies and percents will be computed at each time point by treatment group and separately by participants who were or were not diagnosed with CL-RA.For continuous variable, the number, mean (SD), median, min, and max score will be computed at each planned clinic visit, by treatment arm, and separately for those with and without a prior study-confirmed diagnosis of CL-RA. If any continuous variables that have values below the limit of detection, dichotomous variable will be created and summarize.Summary statistics will also be plotted over time to gain a better understanding of trends.	
Note: All mechanistic data is generated by core laboratory facilities, which may also run analyses.	

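### SAP Table 15 splits continuous antibody levels by prior CL-RA diagnosis, but anti-CCP3 and IgM-RF are not scheduled after diagnosis, so one stratum is essentially empty and the other pools future progressors with non-progressors

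*SAP*

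**What the plan says.** SAP 8.3.7 (Study Objective 8, Table 15) defines three variables, the first being "Levels of anti-CCP3 over time", with IgM-RF and hsCRP treated in the same way. Summaries of continuous variables are "computed at each planned clinic visit, by treatment arm, and separately for those with and without a prior study-confirmed diagnosis of CL-RA". For categorical variables the same table cell uses a different split: by arm, and by whether the participant was ever diagnosed.

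Protocol 8.3.3 summarises dichotomous biomarkers "separately for subjects who do/do not experience clinically-apparent RA". Its sentence on continuous biomarkers also splits by whether an event is or is not experienced, although it names disease reactivation rather than RA.

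On sampling, Protocol 6.5.9 states that, once the Time of Diagnosis visit has taken place, "core outcome specimens (anti-CCP3, IgM-RF, and hs-CRP) will not be collected". The one exception is "HsCRP will be collected at Week 52 and Month 36". The last antibody sample is taken at the Time of Diagnosis visit, where (Protocol 6.5.5.6) "core outcome testing (hsCRP, IgM-RF, and anti-CCP3) and serum for mechanistic studies will be completed".

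**The concern.** The split for continuous levels depends on status at each visit: a participant moves from without to with once CL-RA has been confirmed. SAP Table 14 uses the same idea when it lists diagnosis status at the time of assessment as a model term. Antibody sampling stops at about that same moment. The rule therefore asks for summaries in a stratum where the schedule supplies no antibody data, and it puts every future progressor with the non-progressors for as long as that person is sampled.

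Objective 8 is meant to describe immune responses during RA development and in response to HCQ. For that, the natural display is how levels evolve in people who go on to CL-RA compared with people who do not. For post-baseline continuous levels, Table 15 does not produce it. Table 15 also makes any inferential work on these markers depend on what the descriptive displays suggest.

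**Working it through.** **1. Sampling schedule against the split.** Planned post-baseline core-outcome visits are Weeks 24 and 52 and Months 18, 24, 30 and 36. The visit lists in Protocol 6.5.4 and 6.5.5 and the Schedule of Events footnotes (repeated in SAP 14.2) limit full core sampling to participants not yet diagnosed. For those already diagnosed:

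- anti-CCP3 and IgM-RF: scheduled at 0 of 6 visits;
- hsCRP: scheduled at 2 of 6 visits (Week 52 and Month 36).

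At Baseline nobody has a prior diagnosis.

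**2. Why the rule may have been written this way.** SAP Tables 14, 16 and 17 split by prior diagnosis in much the same words. Joint examinations and the joint-symptom questionnaire continue after diagnosis, so the split can be filled there. It does not carry over to antibodies. SAP section 12 does not list it as a change from Protocol 8.3.3.

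**3. Size, for illustration.** The plan states no figure for this point, so the protocol's own event model is used.

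Inputs: 3-year RA-free survival of 50% (placebo) and 75% (HCQ) with exponential onset (Protocol 8.1); 144 randomised (Interim SAP 5.2.2.1); target days from SAP Table 4, with t = day/365.25 capped at 3. Assumptions: 72 per arm and no dropout.

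Hazard: λ = −ln S(3)/3.

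- Placebo: −ln(0.50)/3 = 0.2310
- HCQ: −ln(0.75)/3 = 0.0959
- Ratio: 2.41

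These reproduce the protocol's 0.231, 0.096 and 2.4.

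Diagnosed by time t: F(t) = 1 − exp(−λt). Share of the not-yet-diagnosed group who progress by Month 36: [F(3) − F(t)] / [1 − F(t)].

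At Week 52, t = 364/365.25 = 0.997:

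- Placebo: F = 20.6%; (0.500 − 0.206)/0.794 = 37.1%
- HCQ: F = 9.1%; (0.250 − 0.091)/0.909 = 17.5%

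| Visit | Already diagnosed, placebo / HCQ (of 72 each) | Total | Future progressors among the undiagnosed, placebo / HCQ |
|---|---|---|---|
| Week 24 | 7.3 / 3.1 | 10.4 | 44.4% / 21.6% |
| Week 52 | 14.8 / 6.6 | 21.4 | 37.1% / 17.5% |
| Month 18 | 21.1 / 9.6 | 30.7 | 29.3% / 13.4% |
| Month 24 | 26.7 / 12.6 | 39.3 | 20.6% / 9.1% |
| Month 30 | 31.6 / 15.3 | 46.9 | 10.9% / 4.7% |
| Month 36 | 36.0 / 18.0 | 54.0 | 0% / 0% |

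The third column counts the participants who would fall in the prior-diagnosis stratum with no scheduled antibody sample. The last column shows how the make-up of the other stratum changes over visits and differs between arms.

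**4. What the alternative split would hold.** Split by diagnosis during the study, the same assumptions give about 54 progressors (36 placebo, 18 HCQ). The number still undiagnosed, and so still sampled, is 54 minus the total column: 54 at Baseline, 43.6 at Week 24, 32.6 at Week 52, 23.3 at Month 18, 14.7 at Month 24 and 7.1 at Month 30.

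**The case against.** The strongest reply is that this is an exploratory table. An empty row is visible to any reader, biases no estimate, and touches no primary or safety result. The SAP also lets core laboratories run analyses and leaves additional mechanistic work to separate plans. That fixes the weight of the point, but it does not make the rule workable.

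Four stronger readings are tempting, and the documents do not support them.

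- *A false HCQ benefit.* A reader might infer that antibody means falling as progressors leave would be taken as benefit. Protocol 6.4.3 interprets levels in the HCQ arm compared with placebo, not a fall over visits. Under the design hazards placebo loses more progressors, so if they have higher titres the artefact would tend to work against HCQ.
- *No contrast of progressors and non-progressors anywhere.* Objective 6 (SAP 8.3.5) compares baseline anti-CCP3, IgM-RF and hsCRP between those who did and did not develop CL-RA. Categorical versions in Table 15 are already split by diagnosis. The gap is post-baseline continuous levels.
- *Literally no value in the stratum.* A Time of Diagnosis visit supersedes a planned visit with which it overlaps, so isolated antibody values could appear there.
- *The sample nearest onset is discarded.* Only the Interim SAP (5.1.2) keeps Time of Diagnosis data out of by-visit summaries, and it covers the interim efficacy and futility analyses. The final Table 15 says all available data are included, but does not say where this sample goes. Core samples are also drawn at any visit with RA-like synovitis, and these enter a by-visit summary when the visit is a planned one.

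One further objection stands and shapes the remedy: splitting by eventual diagnosis conditions on a post-randomisation outcome, and some participants in the not-diagnosed group will have incomplete follow-up.

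**Conclusion.** The point holds for the continuous summaries in SAP Table 15. For anti-CCP3 and IgM-RF the prior-diagnosis stratum has no scheduled sample at any of the six planned post-baseline core visits, apart from a possible isolated Time of Diagnosis value. For hsCRP it has two. The other stratum pools future progressors with non-progressors, so post-baseline continuous levels are never contrasted by outcome.

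That much follows from the text alone. The size depends on the design hazards, 72 per arm, exponential onset and no dropout, and it treats sampling as ending at diagnosis. On that basis about 21% (placebo) and 9% (HCQ) have left antibody sampling by Week 52, and 50% and 25% by Month 36. SAP 5.4 reports that the DSMB recommended stopping for futility, so the actual difference between arms may be smaller than this. With equal hazards the pooling and attrition would remain, and the imbalance between arms would shrink. The consequence is limited to secondary, descriptive analyses.

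**What to change.** In SAP Table 15:

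- Split continuous levels by whether CL-RA was diagnosed during the study, matching the categorical bullet.
- State that the Time of Diagnosis sample is included, and summarise progressors' levels by time before diagnosis.
- Keep the prior-diagnosis split only for hsCRP at Week 52 and Month 36.
- Label the split by eventual status as descriptive natural history, not a randomised comparison of HCQ with placebo.
- Identify participants in the not-diagnosed group with incomplete follow-up, including those whose antibody sampling stopped because they began RA medication after an outside diagnosis (Protocol 6.5.10).
- Record the change in SAP section 12. If the database is already locked, Protocol 8.5.5 calls for documentation in the clinical study report.

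The cost is SAP wording and table shells. Every sample needed is already in the schedule.

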8.4. Exploratory Endpoints

Exploratory endpoints that are not directly related to a specific study objective are included with the planned estimands.

8.4.1. Physician-reported Joint Counts

Physicians use the Physician Joint Exam at every clinic visit to identify tender and swollen joints. These data are used to count the number of (1) tender and (2) swollen joints.

Table 16: Estimands of Physician-reported Joint Counts

Estimate Label	Count Variables
Secondary 9.1	Number of physician-identified tender joints at each clinic visit
Secondary 9.2	Number of physician-identified swollen joints at each clinic visit
Population: mITT	IES Policy: All available study data will be included.
Population Level Summary: Population Level Summary: At each planned clinic visit, the number, and percent of individuals with physician-identified tender joints (or swollen joints) will be computed by treatment arm, and separately for those with and without a prior study-confirmed diagnosis of CL- RA. Among those with tender (or swollen joints), mean, median, min and max # of affected joints will also be reported. Summary statistics will also be plotted over time to gain a better understanding of trends.	Analysis: At Week 52 and Month 36/EOS, Mann-Whitney U statistics will be used to compare joint counts between treatment arms, separately for those with and without a diagnosis of CL-RA. Because the distributional characteristics these variables are unknown, we cannot prespecify the planned analysis strategy. However, in this population, it is reasonable to expect there will be excess # of participant visits where no tender joints (or swollen joints) are identified. If this is the case, it may appropriate to fit a longitudinal zero-inflated negative binomial model with the number of involved joints as the dependent variable and treatment arm as the primary fixed effect. Important additional fixed effects to consider would include prior CL-RA diagnosis at time of assessment (Y/N), study day (or visit), treatment period (on study drug vs off study drug), duration on study treatment, and interaction terms for treatment arm, prior CL-RA diagnosis, and study day (or visit). Heterogeneous random participant effects could be included in the model per the methods of Zhu et al [4], and relevant covariates included in the regression on the covariance matrix will be determined. T-tests for the maximum likelihood estimates of the model parameters could be used to determine the significance of the parameters to the model.
Note: Modeling will be exploratory and only initiated if descriptive analyses suggest interesting trends.	

8.4.2. Disease Activity Assessments

The DAS28-CRP score is calculated from the tender and swollen joint counts from the Physicians Joint Exam, the laboratory result for hsCRP and the Overall Health score from the MDHAQ. The score will be calculated at the visits where the real-time core outcome hsCRP sample was collected.

The CDAI score is calculated from the tender and swollen joint evaluations in the Physicians Joint Exam, the Overall Health score from the MDHAQ assessment and the Physicians Global Assessment of Overall Disease Activity in the Physicians Assessment.

The SDAI score is calculated from the tender and swollen joint evaluations in the Physicians Joint Exam, the Overall Health score from the MDHAQ assessment and the Physicians Global Assessment of Overall Disease Activity in the Physicians Assessment, and the hsCRP level.

The RAPID-3 score is calculated from the MDHAQ assessment.

Autoimmunity Centers of Excellence
Statistical Analysis Plan – ARA08 StopRA

NIH PROMIS Profile 29 is a patient reported outcome (PRO) assessment with multiple modules that are used to calculate the Physical Health score, Mental Health score, and Social Health score. The score will be calculated at the visits when the PROMIS Profile 29 assessments were conducted. The PROMIS Profile 29 scores will be calculated using a validated scoring method (https://www.healthmeasures.net/index.php?option=com_content&view=category&layout=blog&id=190&Itemid=1214)

Table 17: Estimands of Disease Activity Assessments

Estimate Label	Scale Score Variables
Secondary 9.3	DAS28-CRP score at each clinic visit.
Secondary 9.4	CDAI at each clinic visit.
Secondary 9.5	RAPID-3 score at each clinic visit.
Secondary 9.5	PROMIS Profile 29 Physical health score at each clinic visit.
Secondary 9.6	PROMIS Profile 29 Mental health score at each clinic visit.
Secondary 9.7	PROMIS Profile 29 Social health score at each clinic visit
Population: mITT	IES Policy: All available study data will be included.
Population Level Summary: At each planned clinic visit, the number, mean (SD), median, min, and max score will be computed by treatment arm, and separately for those with and without a prior study-confirmed diagnosis of CL- RA. Summary statistics will also be plotted over time to gain a better understanding of trends.	Analysis: At Week 52 and Month 36/EOS, Mann-Whitney U statistics will be used to compare scores between treatment arms, separately for those with and without a diagnosis of CL-RA. If data are consistent with a Gaussian distribution, the data may be analyzed using a repeated measure mixed regression model with the scale score variable at each visit as the dependent variable and treatment arms as the primary fixed effect. Important additional fixed effects to consider would include prior CL-RA diagnosis at time of assessment (Y/N), study day (or visit), treatment period (on study drug vs off study drug), duration on study treatment, and interaction terms for treatment arm, prior CL-RA diagnosis, and study day (or visit). Random participant effects may include random intercepts and/or slopes for each participant
Note: Modeling will be exploratory and only initiated if descriptive analyses suggest interesting trends.	

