6.5.3 Baseline/Randomization Visit

The baseline evaluations must be performed within 30 days of the Screening visit.

1. Medical History
2. Prior/Concomitant Medications
3. Physical Exam (symptom-driven)
4. Vital Signs including heart rate and sitting systolic/diastolic blood pressure
5. STAT Urine pregnancy test (for women of child-bearing potential)
6. Joint Examination – Physician's Assessment (including a swollen/tender joint count). *Note: The count will include 66 tender/64 swollen joints.*
 - *The ankle joint(s) on each limb will be counted as a single joint that includes the talo-tibial joint (also called the talo-crural joint), subtalar joint (also called talo-calcaneal joint), and inferior tibio-fibular joint.*
 - *The midfoot joints will not be evaluated for either tenderness or swelling.*
 - *The hip joints will not be evaluated for swelling.*
7. Randomization

IMPORTANT: Subjects with tender joints and/or swollen joints that are consistent with RA-like synovitis at the time of the Baseline/Randomization Visit should NOT be randomized or treated.

Note: Sites utilizing a central pharmacy may randomize subjects prior to the Baseline visit after initial eligibility at Screening has been confirmed, but if tender joints and/or swollen joints that are consistent with RA-like synovitis are noted at baseline, do NOT dispense the study medication to the subject.

8. Subject Questionnaires
 - Profile 29 v2.0
 - Epidemiologic Questionnaire
 - Dietary Assessment Questionnaire
 - Self-reported Joint Symptoms, including modified MDHAQ
 - Evaluate family member participation
9. Specimen collection for **real-time** core outcome testing (hsCRP, IgM-RF, Anti-CCP3) and serum for mechanistic studies.
10. Specimen collection for mechanistic studies: PBMC/plasma, RNA, and urine. *Note: DNA will be collected from subjects who consent to the optional specimen for shared epitope analysis.*
11. Dispense study therapy

Notes:

- *Female subjects cannot receive study therapy until eligibility can be confirmed via STAT urine pregnancy test.*
- *The first dose of study therapy will be given in clinic. The subject will be observed per institutional standards.*

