6.5.4.2 Mid-Treatment Clinic Visit: Week 24 (Visit Windows: +/- 7 days)

1. AE Assessment
2. Concomitant Medications
3. Physical Exam (symptom-driven)
4. Vital Signs including heart rate and sitting systolic/diastolic blood pressure
5. Hematology: Hemoglobin, hematocrit, WBC (with differential), and platelet count
6. Chemistry: Serum creatinine, ALT, and AST

Note: Abnormal lab values meeting the criteria noted in Section 5.8.1, *Study Treatment Discontinuation*, should be confirmed within 4 weeks, prior to discontinuation.

7. Self-reported Joint Symptoms, including modified MDHAQ
8. Joint Examination – Physician’s Assessment (including a swollen/tender joint count). *Note: The count will include 66 tender/64 swollen joints.*
 - *The ankle joint(s) on each limb will be counted as a single joint that includes the talo-tibial joint (also called the talo-crural joint), subtalar joint (also called talo-calcaneal joint), and inferior tibio-fibular joint.*
 - *The midfoot joints will not be evaluated for either tenderness or swelling.*
 - *The hip joints will not be evaluated for swelling.*
9. Evaluate family member participation

Items 10-14 are only applicable to subjects who have not been diagnosed with clinically-apparent RA at a prior visit.

10. Procedures conditional on results of the Joint Examination
 - If the subject **has 1 or more** swollen joints that are consistent with RA-like synovitis, refer to protocol section 6.5.9, *Evaluations Triggered by a Swollen Joint*, for a list of additional assessments that are required to be completed at this visit.
 - If the subject **does not have** a swollen joint that is consistent with RA-like synovitis;
 - Specimen collection for **future** core outcome testing (hsCRP, IgM-RF, and anti-CCP3) and serum for mechanistic studies
11. Specimen collection for HCQ Level analysis
 - *Note: This specimen will be collected at the Week 24 visit, provided the specimen was not collected previously.*
12. Subject self-reported pregnancy status
13. Dispense study therapy

14. Pill Counts (at each clinic visit)

6.5.4.3 **End of Treatment: Week 52 (Visit Window: +/- 14 days)**

1. AE Assessment
2. Concomitant Medications
3. Physical Exam (full)
4. Vital Signs including heart rate and sitting systolic/diastolic blood pressure
5. Subject Questionnaires
 - Profile 29 v2.0
 - Self-reported Joint Symptoms, including modified MDHAQ
 - Evaluate family member participation

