6.5.9 Evaluations Triggered by a Swollen Joint

At any study visit, either regularly scheduled or unscheduled, if a swollen joint(s) that is consistent with RA-like synovitis is identified during the joint examination, the following items will be completed **during the study visit**:

- Specimen collection for **real-time** core outcome testing: hsCRP, IgM-RF, and anti-CCP3 and serum for mechanistic studies
- Specimen collection for mechanistic studies (at the initial occurrence of RA-like synovitis only): PBMC/plasma RNA, and urine. *Note: DNA will be collected from subjects who consent to future genetic testing.*
- X-rays will be performed (at the first occurrence and every 6 months thereafter, if applicable). See protocol section 6.2.3.5, *X-ray Imaging*, **prior** to conducting x-rays on female subjects (who have the ability to become pregnant).
- A follow-up visit will be scheduled within the next 3 to 6 weeks. This visit may coincide with a regularly scheduled visit or may be conducted as an unscheduled visit.
- *Note: Subjects will continue to take study medication until the diagnosis of clinically-apparent RA has been confirmed and the subject returns to the site for a Time of Diagnosis Visit (see Section 6.5.5.6, Time of Diagnosis Clinic Visit).*

After the study visit, once the results from the core outcome tests and x-ray are available, the score for the 2010 ACR/EULAR Classification Criteria will be calculated, and at the 3-6 week follow-up visit, the following may occur:

- 1) If the subject has definite RA per the 2010 ACR/EULAR Classification Criteria (i.e. score ≥ 6), the follow-up visit will become a Time of Diagnosis visit (refer to Section 6.5.5.6, *Time of Diagnosis Clinic Visit*).
- 2) If a swollen joint consistent with RA-like synovitis is identified by joint examination, the ACR/EULAR score is <6 , and x-rays identify the presence of at least 1 erosion the follow-up visit will become a Time of Diagnosis visit (refer to Section 6.5.5.6, *Time of Diagnosis Clinic Visit*).

Note: After the Time of Diagnosis visit, the subject will resume routine study clinic visits in order to follow the natural history of RA; with the following exceptions:

- Scheduled telephone assessments at Weeks 18, 30, and 42, and Months 15, 21, 27, and 33 will not occur.

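### DAS28-CRP is tied to real-time hsCRP, so at seven of ten clinic visits it exists only for people with a swollen joint or not at all, while stored hsCRP at four of those visits goes unused

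*SAP*

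**What the plan says.** SAP 8.4.2 builds DAS28-CRP from the physician joint counts, hsCRP and the overall health score, and then restricts it: "The score will be calculated at the visits where the real-time core outcome hsCRP sample was collected". Table 17 defines the variable (Secondary 9.3) as "DAS28-CRP score at each clinic visit" and gives this population-level summary: "At each planned clinic visit, the number, mean (SD), median, min, and max score will be computed by treatment arm". The summaries are also split by prior study-confirmed RA and plotted over time. For inference, "At Week 52 and Month 36/EOS, Mann-Whitney U statistics will be used to compare scores between treatment arms". A repeated-measures mixed model may follow if the data look Gaussian and the descriptive results suggest something of interest.

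The protocol separates two kinds of hsCRP sample. Real-time testing is scheduled at Baseline ("Specimen collection for real-time core outcome testing (hsCRP, IgM-RF, Anti-CCP3) and serum for mechanistic studies"), Week 52 and Month 36. It is also triggered at any visit where an undiagnosed participant has a swollen joint (Protocol 6.5.9: "Specimen collection for real-time core outcome testing: hsCRP, IgM-RF, and anti-CCP3 and serum for mechanistic studies"). At Week 24 and Months 18, 24 and 30, undiagnosed participants without a swollen joint instead give a specimen for future testing, covering "core outcome testing (hsCRP, IgM-RF, and anti-CCP3) and serum for mechanistic studies". The SAP plans to use hsCRP as a longitudinal variable in its own right: Secondary 8.3 is "Levels of hsCRP over time".

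**The concern.** Two statements in one SAP section do not fit together. One calls for DAS28-CRP at every clinic visit; the other allows it only where hsCRP was run in real time. At most visits, whether hsCRP was run in real time depends on a joint finding made after randomization. The swollen joint count is itself a term in DAS28-CRP, and a swollen joint is the inflammatory arthritis endpoint of SAP 8.3.2. If the rule is applied to each participant's own samples, the plotted curve would run from everyone at Baseline, to swollen-joint participants only through Week 36, back to everyone at Week 52, and would repeat that pattern up to Month 36. Any rise and fall it showed could come from who is included. A mixed model would not repair this, because a score would be missing according to a component of the unobserved score.

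Protocol 6.2.3.1 names DAS28-CRP as the main disease activity measure, and Protocol 3.3.1 lists its trends over the treatment and follow-up periods as secondary endpoints. The restriction to real-time samples does not appear among the changes from the protocol in SAP section 12.

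**Working it through.** The plan states no figure to reproduce. The check is a count of planned clinic visits by type of hsCRP sample, taken from Protocol 6.5.3, 6.5.4.1 to 6.5.4.3, 6.5.5.2 to 6.5.5.5, 6.5.9 and 6.5.10.

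| Visit | Undiagnosed, no swollen joint | Undiagnosed, swollen joint | Prior clinically-apparent RA |
|---|---|---|---|
| Baseline | real-time | not to be randomized or treated | not applicable |
| Weeks 6, 12, 36 | none | real-time | none |
| Week 24 | stored | real-time | none |
| Week 52 | real-time | real-time | real-time |
| Months 18, 24, 30 | stored | real-time | none |
| Month 36 | real-time | real-time | real-time |

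**Counts**
- Planned clinic visits: 1 + 3 + 1 + 1 + 3 + 1 = 10.
- Real-time hsCRP scheduled for everyone: 3 (Baseline, Week 52, Month 36).
- Real-time hsCRP only for undiagnosed participants with a swollen joint: 10 − 3 = 7, which is 7/10 = 70% of all visits and 7/9 = 78% of post-baseline visits.
- Of those 7, a stored sample exists for the other undiagnosed participants at 4 (Week 24, Months 18, 24 and 30; 4/7 = 57%). At the remaining 3 (Weeks 6, 12 and 36) there is no hsCRP sample of any kind.

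**Effect of the rule under each reading**
- *Per participant:* at seven visits the stratum without prior RA consists only of people with a swollen joint, and the stratum with prior RA is empty.
- *Scheduled visits only:* scores exist at Baseline, Week 52 and Month 36. Each protocol-defined period then has two points: Baseline and Week 52 for treatment, Week 52 and Month 36 for follow-up.

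**Effect of using stored results.** Visits covering undiagnosed participants with and without a swollen joint rise from 3 to 3 + 4 = 7 of 10.

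**Direction and scale.** In Protocol 15.3 the swollen-joint term is 0.28 × √SJC28, so one swollen joint among the 28 adds 0.28 × √1 = 0.28 to a person's score. The other terms are unknown. The documents give no rate of swollen joints by visit. Purely as an assumption, if 2% to 20% of the 144 randomized participants (interim SAP 5.2.2.1) had a swollen joint at a visit, the affected mean would rest on 144 × 0.02 = 2.9 to 144 × 0.20 = 28.8, or about 3 to 29 people over both arms. Attrition and earlier diagnoses would lower these numbers.

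**The case against.** The strongest reply is that the restriction refers to scheduled real-time visits, so no selected means would ever be produced. There is support for this. Schedule of Events Tables 6.1 and 6.2 put swollen-joint evaluations in a column of their own. Protocol 6.5.10 says that Week 52 and Month 36 hsCRP in participants treated after an outside diagnosis is collected to evaluate DAS28-CRP. SAP 8.4.2 limits PROMIS in parallel words to the visits where it was administered, yet Table 17 also lists PROMIS at each clinic visit, so that phrase may be generic. This reading is tenable, and it cannot be said that selected means will be reported. It does not close the point: the SAP does not say which reading applies, and the scheduled-visit reading leaves three time points and passes over stored samples.

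It is also fair that the stakes are modest. SAP 8.4 places these analyses under exploratory endpoints, secondary p-values are descriptive, CDAI and RAPID-3 need no CRP, and the number of scores per visit would be shown, so small subsets would be visible.

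Three stronger inferences are not supported:
- A reader might conclude that the arms will be formally compared in outcome-selected subsets. The Mann-Whitney tests are at Week 52 and Month 36, where real-time hsCRP is scheduled for everyone. Only descriptive summaries, plots and an optional model are exposed.
- A reader might suppose that stored samples exist for everyone else. They exist at four of the seven visits, and not for participants with prior RA.
- A reader might put assumed patients through the DAS28-CRP formula and report a large gap between selected and full means. The documents give no joint counts, hsCRP, global health values or swollen-joint rates by visit, so such a gap would reflect the chosen profiles.

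**Conclusion.** The point holds as an inconsistency with a better method available on either reading. Read per participant, the rule selects on a component of the score at seven of ten visits. Read by scheduled visit, it reduces the planned trends to three time points. In both cases four visits with stored hsCRP are lost. The size of any distortion cannot be derived from the documents, and the planned between-arm tests stand.

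The conclusion assumes that samples are collected as scheduled and that the stored samples will be assayed. Protocol 6.4.3 and Secondary 8.3 support the second assumption, although neither says when the assays will be done. Stored material is a reasonable source: Protocol 1.1.2.4 favours hsCRP partly for its stability in stored samples, and SAP 8.4.2 defines SDAI from hsCRP with no real-time restriction. This is worth correcting but does not bear on the primary analysis.

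**What to change.** Amend SAP 8.4.2 and Table 17 as follows.

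1. Calculate DAS28-CRP wherever an hsCRP result is available, real-time or stored. For participants without prior clinically-apparent RA, use the stored-sample results planned for Secondary 8.3 at Week 24 and Months 18, 24 and 30.
2. Leave Weeks 6, 12 and 36 out of the DAS28-CRP summaries, plots and model, because no hsCRP is drawn then from participants without a swollen joint.
3. For participants with prior clinically-apparent RA, report DAS28-CRP at Week 52 and Month 36 only. If a mixed model is fitted, state that they have no hsCRP at the other visits.
4. List in Table 17 the visits at which DAS28-CRP is defined, in place of each clinic visit.

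The same change would help at the Time of Diagnosis visit, where Protocol 6.5.5.6 collects a sample for future testing and SAP section 10 names DAS28-CRP as a possible measure of severity at diagnosis.

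The cost is a wording change, with no new sampling. The one small downside is that the stored-sample assays must be complete before the final analysis.
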